^b Enrollment up to 30 subjects is permitted if additional subjects are necessary for safety or PK evaluations.

Study Assessments

Subjects will be monitored for safety, tolerability, PK and immunogenicity of BGB-DXP593 throughout the study.

Assessments of safety will include adverse events (AEs), SAEs, clinical laboratory tests, physical examinations, vital signs, and ECGs. A Safety Monitoring Committee (SMC) will periodically monitor safety data.

Adverse events will be graded for severity per the current version of the National Cancer Institute Common Terminology Criteria for Adverse Events (NCI-CTCAE) version 5.0. Refer to Section 9 for additional and specific information regarding AE monitoring and reporting.

PK and ADA sampling will be collected at specific intervals from Day 1 to Day 113 (Appendix 3).

Study procedures and assessments are further detailed in Section 7 and Section 8, respectively, and the Schedule of Assessments can be found in Appendix 1. Specific details regarding dose escalation are described in the following sections.

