8.4. Visit Windows

The PK sampling schedule allows for a visit window of ± 1 day for the visits at Day 15, Day 22 and Day 29, and a visit window of ± 2 days for the visits at Day 43, Day 57, Day 71, Day 85, and Day 113 ([Appendix 1](#) and [Appendix 3](#)). All assessments will be performed on the day of the specified visit.

8.5. **Unscheduled Visits**

Unscheduled visits may be performed at any time at the subject's or investigator's request if there are any safety concerns. The date and reason for the unscheduled visit must be recorded in the source documentation.

If an unscheduled visit is necessary to assess toxicity, then diagnostic tests may be performed based on the investigator's assessment as appropriate, and the results of these tests should be recorded on the unscheduled visit eCRF.

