2. STUDY OVERVIEW

This is a first-in-human, randomized, double-blind, placebo-controlled, single dose escalation study to investigate the safety, tolerability, pharmacokinetic (PK), and immunogenicity of BGB-DXP593 in healthy subjects.

Two dose levels are planned for eligible subjects to receive a single intravenous dose of study drug (ie, BGB-DXP593 or placebo) at 10 mg/kg or 30 mg/kg, respectively. Another higher dose level will be allowed for dose escalation.

Enrollment will begin at the 10 mg/kg dose level. Escalation to the next dose level will occur 7 days after the last subject at the current dose level has received the study drug, and the safety, laboratory data have been reviewed.

At each dose level, eligible subjects will be randomized at a 3:1 ratio (6 active: 2 control) to the active arm for receiving BGB-DXP593 or to the control arm for receiving the same volume of placebo (ie, normal saline), respectively.

The sentinel dosing will be adopted for each dose level. In the other words, 2 eligible subjects will be randomized at a 1:1 ratio (1 active: 1 control) to receive BGB-DXP593 or placebo on Day 1; and the remaining subjects will be randomized at a 5:1 ratio (5 active: 1 control) to receive BGB-DXP593 or placebo at least 48 hours later, provided satisfactory safety and tolerability is demonstrated for the first 2 subjects randomized and dosed at the dose level.

Subjects are expected to be available for follow-up visits until Day 113 of the study. Subjects will be replaced if they cannot complete the infusion. Subjects may be replaced if they discontinue from the study before Day 29.

Subjects will be monitored for safety, tolerability, PK and immunogenicity of BGB-DXP593 throughout the study.

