6.7. Immunogenicity Analyses

The scope of anti-drug antibodies (ADA) calculations used for characterizing clinical immunogenicity depends on the incidence and kinetics of detected (ADA). Therefore, not all parameters described below may be derived.

The immunogenicity results will be summarized using descriptive statistics by the number and percentage of subjects who develop detectable ADAs. The incidence of positive and neutralizing ADAs will be reported for ADA-evaluable subjects according to the following definitions:

- ADA-evaluable subject: Number of subjects with reportable non-missing baseline result
 and at least one reportable sample taken after drug administration during the treatment or
 follow-up observation period with reportable result (used for computing treatmentinduced ADA incidence).
- Treatment-emergent ADA: Treatment-boosted ADA subject or treatment-induced ADA subject. Synonymous with "ADA Incidence".
- Treatment-induced ADA: ADA-evaluable subjects that were ADA-negative at baseline and ADA-positive following administration of biologic product.
- Treatment-boosted ADA: Baseline-positive ADA-evaluable subject with significant increases (4-fold or higher) in ADA titer after biologic drug administration. [Baseline-positive ADA-evaluable subject: an ADA-evaluable subject with positive ADA result].
- Persistent ADA: Treatment-induced ADA detected at two or more sampling time points during the treatment (including follow-up period if any), where the first and last ADA-positive samples (irrespective of any negative samples in between) are separated by a period of 16 weeks or longer.
- Transient ADA: Treatment-induced ADA detected only at one sampling time point during the treatment or follow-up observation period, or two or more time points during the treatment, where the first and last ADA-positive samples are separated by a period of less than 16 weeks, and the subject last sampling time point is ADA-negative.
- Neutralizing ADA: subjects with positive NAb.

The immunogenicity results will also be listed.

Additional ADA analyses (such as the effect of immunogenicity on PK, and safety) may be conducted if deemed necessary and will be described in a separate analysis plan.

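### As worded, SAP 6.7 calls ADA 'transient' when the only positive is the last sample, although no later sample shows that it cleared

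*SAP*

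**What the plan says.** SAP Section 6.7 (Immunogenicity Analyses) applies the duration classes to treatment-induced ADA, meaning "ADA-evaluable subjects that were ADA-negative at baseline and ADA-positive following administration of biologic product". Two classes matter here.

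- **Persistent**: positive at two or more time points, where the first and last positives "are separated by a period of 16 weeks or longer".
- **Transient**, first limb: "Treatment-induced ADA detected only at one sampling time point during the treatment or follow-up observation period". **Transient**, second limb: two or more time points, "where the first and last ADA-positive samples are separated by a period of less than 16 weeks, and the subject last sampling time point is" negative.

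The same section says that some of the listed ADA parameters may not be derived, and that immunogenicity results will also be listed.

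On timing, SAP Section 2 says: "Subjects are expected to be available for follow-up visits until Day 113 of the study". Protocol Section 3.1 says: "PK and ADA sampling will be collected at specific intervals from Day 1 to Day 113". Protocol Appendix 3 places the ADA draws at predose and on Days 15, 29, 57, 85 and 113/EOS. No later ADA draw is scheduled.

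**The concern.** Calling ADA transient says that it appeared and then went away. The second limb respects this by asking for a negative final sample. The first limb does not ask for it, and it expressly includes the follow-up period, so it takes in a positive found only at the final draw. For that subject the data show onset and nothing about duration.

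The result is uneven. A subject positive at Days 85 and 113 gets no class, while a subject positive at Day 113 alone is called transient, yet both end the study positive. At stake is whether the reported transient count means what its name says. Immunogenicity is a secondary objective, and the endpoint is detection of ADA over time.

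**Working it through.** The documents give no figure for these classes, so there is none to reproduce. The check applies the definitions to the sampling schedule.

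**Inputs**
- Post-dose ADA samples at 336, 672, 1344, 2016 and 2688 hours, that is Days 15, 29, 57, 85 and 113 (Protocol Appendix 3).
- Windows: ±1 day at Day 15, and "a visit window of ± 2 days for the visits at Day 43, Day 57, Day 71, Day 85, and Day 113" (Protocol Section 8.4).
- Class definitions from SAP Section 6.7. The second transient limb mentions only the treatment period. I take it to include follow-up, because this is a single-dose study and every post-dose ADA sample falls in follow-up.

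**Step 1. Which limb carries the last-sample condition?** The clause "and the subject last sampling time point is ADA-negative" continues a phrase about the gap between first and last positive samples. That phrase presupposes two distinct positives, so it belongs to the two-or-more limb. Call this reading A. Reading B lets the clause close both limbs.

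**Step 2. Can any scheduled pattern be persistent?** A treatment-induced subject is negative at baseline, so the longest span between positives is Day 15 to Day 113: (2688 − 336)/24 = 98 days = 14.0 weeks. With both windows at their extremes it is 98 + 1 + 2 = 101 days, or 101/7 = 14.4 weeks. Both are below 16 weeks, so the persistent class is empty on the planned schedule.

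**Step 3. Classify every pattern.** Five samples give 2^5 − 1 = 31 patterns with at least one positive.
- Last sample negative: 2^4 − 1 = 15 patterns.
- Last sample positive: 2^4 = 16 patterns, of which 1 is Day 113 alone and 15 have an earlier positive as well.

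| Rule | Transient | Persistent | No class | Positive at last sample, own class | Day 113 only | Days 85 and 113 |
|---|---|---|---|---|---|---|
| Reading A | 15 + 1 = 16 | 0 | 15 | – | transient | no class |
| Reading B | 15 | 0 | 1 + 15 = 16 | – | no class | no class |
| Proposed rule, threshold still 16 weeks | 15 | 0 | 0 | 16 | own class | own class |

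These are counts of possible patterns, not probabilities. The same logic applies to a subject who leaves early and whose only positive is the EOS sample.

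**Step 4. Is a first positive at Day 113 to be expected?** I used the human projection in Protocol Table 1 (CL 0.0075 L/h, Vc 2.96 L, Q 0.033 L/h, Vp 2.41 L) and assumed 70 kg, 10 mg/kg and a 1-hour infusion.
- k10 = 0.0075/2.96 = 0.00253 per h; k12 = 0.033/2.96 = 0.01115 per h; k21 = 0.033/2.41 = 0.01369 per h.
- The terminal rate β is the smaller root of x² − (k10 + k12 + k21)x + k10·k21 = 0, which is 0.00133 per h, a half-life of about 22 days.
- Projected serum drug is 8.1 µg/mL at Day 85 and 3.3 µg/mL at Day 113, a fall of about 2.4-fold.

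The subject in question is negative to Day 85 and positive at Day 113, so this is the interval that matters. The documents give neither the assay's drug tolerance nor an expected ADA rate, so the projection cannot be turned into an expected number of such subjects.

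**Step 5. Weight of one subject.** With 6 active subjects per dose level, one is 1/6 = 17% of that arm.

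**The case against.** Four objections deserve an answer.

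*The sentence can be read the other way.* The last-sample clause follows a comma and could be meant to close both limbs. This is possible, though less natural. On that reading the Day-113-only subject is unclassified rather than called transient, so the definition still fails for that subject, and two programmers could code it differently.

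*The category may never be tabulated.* The SAP commits to the incidence of positive and neutralizing ADA, warns that some parameters may not be derived, and lists the results. This stands, and it limits the consequence: a late positive stays visible by subject.

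*A reader might infer that the rule biases the persistence conclusion in the drug's favour.* The documents do not support that. No scheduled pattern can reach the persistent class with or without this rule, so the persistent count does not move. Treatment-emergent ADA incidence and neutralizing ADA do not move either.

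*A reader might also infer that a first positive at the final draw is likely, because drug in the sample is lowest then.* The same projection gives 75.7 µg/mL at Day 15, a 23-fold fall by Day 113, which looks persuasive. Most of that fall is over by Day 85, when a sample is already taken, and only about 2.4-fold remains. Late first detection is conceivable if the assay is sensitive to circulating drug, but that is an assumption. The figure of 1 in 6 likewise reflects the cohort size and does not measure the defect. The label is best described as unsupported, because the true duration is unknown.

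**Conclusion.** The point holds as a small drafting defect. On the natural reading of SAP Section 6.7, ADA seen only at the last sample is called transient without evidence of clearance. On the alternative reading it has no class. Nothing else in the protocol or SAP settles the case.

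The effect is confined to the transient count, and arises only if that class is reported. Its size is the number of subjects first positive at their last draw, which cannot be estimated from the documents. The conclusion rests on the scheduled sampling days and on the grammar of one sentence; it does not depend on the pharmacokinetic projection.

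**What to change.** Rewrite the duration classes together, in the same edit that corrects the unreachable 16-week threshold. Changing the threshold alone would leave the first transient limb as it is.

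- **Transient**: treatment-induced ADA with a negative last sample, and either one positive time point or two or more whose first-to-last span is below the persistence threshold.
- **Indeterminate duration / not resolved at last sample**: any treatment-induced subject who is positive at the last available sample and does not meet the persistent definition, with one positive or several.

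The second category must cover multi-positive subjects. If it took only those positive at the last sample alone, the 15 patterns with an earlier positive as well would still have no label. State also that the last sample is the last one actually obtained, so that an early EOS visit is handled in the same way.

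The cost is a few sentences in the SAP, one more category wherever duration classes are shown, and possibly a lower transient count. No extra samples or visits are needed.

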7. INTERIM ANALYSIS

There is no formal interim analysis planned for this study.

8. CHANGES IN THE PLANNED ANALYSIS

Not applicable.

BeiGene 12 May 2021

APPENDIX A. IMPUTATION OF MISSING OR PARTIALLY MISSING DATES

In general, missing or partial dates will not be imputed at the data level. The following rules will apply for the specific analysis and summary purposes mentioned below only.

1. Adverse Events

If AE start (onset) date or end date is missing or partial missing, the following imputation rules apply.

If end date of an adverse event is partially missing, impute as follows:

- If both month and day are missing, then set to December 31
- If only day is missing, then set to last day of the month
- If the imputed end date > death date, then set to death date

If year of the end date is missing or end date is completely missing, do not impute.

If start date of an adverse event is partially missing, impute as follows:

- If both month and day are missing and year = year of treatment start date, then set to treatment start date
- If both month and day are missing and year ≠ year of treatment start date, then set to January 01
- If day is missing and month and year = month and year of treatment start date, then set to treatment start date
- If day is missing and month and year ≠ month and year of treatment start date, then set to first of the month
- If the imputed start date > death date, then set to death date

If year of the start date is missing or start date is completely missing, do not impute.

If the imputed start date > the end date (or the imputed end date), set the imputed start date = end date (or the imputed end date).

2. Prior/Concomitant Medications/Procedures

When the start date or end date of a medication/procedure is partially missing, the date will be imputed to determine whether the medication/procedure is prior or concomitant. The following rules will be applied to impute partial dates for medication/procedure:

If start date of a medication/procedure is partially missing, impute as follows:

- If both month and day are missing, then set to January 01
- If only day is missing, then set to the first of the month
- If the imputed start date > death date, then set to death date

If end date of a medication/procedure is partially missing, impute as follows:

• If both month and day are missing, then set to December 31

BeiGene 12 May 2021

- If only day is missing, then set to last day of the month
- If the imputed end date > death date, then set to death date

If the year of start date or year of end date of a medication/procedure is missing, or the start date or end date is completely missing, do not impute.
